8.3 Study Periods Relative to Treatment

8.3.1 Time in Relation to Treatment

Adverse events, serious adverse events, death, laboratory data, vital signs will be assigned to the study time periods defined below. Partial dates will be imputed into full dates for AE start date and concomitant medication start and end dates, (see [Section 8.1.3](#)) for assigning data to the appropriate study periods.

Pre-therapy is defined as the time prior to the first dose of study treatment.

On-therapy is defined as the time from the start of first infusion to one week following the end of the last infusion of study treatment.

Post-therapy is defined as any time beyond the on-therapy period to completion of the study. The first dose day (Day 1) is considered to be on-therapy for adverse events and concomitant medications.

8.3.2 Study Time Periods for Medications

Prior ACS-related medications taken by subjects in the 4 weeks before screening will be captured in a targeted manner. All medications taken or administered at any time during the time from informed consent through Visit 8/Day 90 will be collected. Medications contributing to or used in the treatment of an SAE will be collected through the EoS. For the purpose of summarizing medications usage during the study, the following designation will be used: “Concomitant”, defined based on a 90-Day window and “Concomitant through End of Study”.

Designate as “Concomitant” if the medication *start* date is before study day 90 and any of the following conditions is met:

- If the medication *end* date is after the study treatment start date
- If the medication *end* date is missing
- If the study treatment start date is missing

Designate as Concomitant through End of Study” if the medication *start* date is before subject’s last contact date and any of the following conditions is met:

- If the medication *end* date is after the study treatment start date
- If the medication *end* date is missing
- If the study treatment start date is missing

Medication usage will be also categorized relative to first dose of investigational product as described below.

Start date relative to treatment

- Assigned to 'BEFORE' if the medication start date is prior to study treatment start date; or if subject has not taken any study treatment; or the medication start date is missing and the medication end date is before the study treatment start date.
- Assigned to 'DURING' if the medication start date falls into the on-therapy period as defined in [Section 8.3.1](#) or the medication start date is missing.

- Assigned to 'AFTER' if the medication start date is after the on-therapy period defined in [Section 8.3.1](#).

End relative to treatment

- Assigned to 'BEFORE' if the medication end date is prior to study treatment start date or if the subject has not taken any study treatment.
- Assigned to 'DURING' if the medication end date falls into the on-therapy period; or the medication end date is missing and the medication start date relative to treatment is not assigned to 'AFTER').
- Assigned to 'AFTER' if the medication end date is after the on-therapy period or the medication end date is missing and the medication start relative to treatment is assigned to AFTER'.

Baseline medications:

Any medication that started on or prior to the date of first infusion and the end date is either after the date of first infusion or missing (implying the medication is ongoing) is defined as a baseline medication.

8.4 Values of Potential Clinical Importance

8.4.1 Laboratory Parameters

A laboratory value that is outside the reference or the normal range can be categorized as either a high abnormal value (a value above the upper limit of the normal [ULN]) or low abnormal value (a value below the lower limit of the normal). A laboratory parameter can take on both high and low abnormal values at different Safety assessment visits. Note that a laboratory value outside the reference range is not necessarily one of potential clinical importance.

Specific laboratory values of potential clinical importance are those that exceed the thresholds defined below:

Absolute change from baseline in serum creatinine during the Active Treatment Period will be categorized based on SI units of $\mu\text{mol/L}$. Equivalent conventional units are shown for descriptive purposes:

$\geq 27 \mu\text{mol/L}$ to $\leq 44 \mu\text{mol/L}$ (≥ 0.3 to $\leq 0.5 \text{ mg/dL}$)

$> 44 \mu\text{mol/L}$ ($> 0.5 \text{ mg/dL}$)

Increases in serum creatinine relative to baseline value:

$\geq 1.5x$ baseline value

$\geq 2.0x$ baseline value

$\geq 3.0x$ baseline value

Raw serum creatinine value $\geq 354 \mu\text{mol/L}$ (4.0 mg/dL)

A decrease in eGFR $\geq 25\%$ from baseline during the active treatment period

Changes in hepatic status occurring at any time during the study:

ALT $> 3x$ ULN

ALT $> 5x$ ULN

ALT $> 10x$ ULN

Serum TBili[†] $> 2x$ ULN

[†] Note that for subjects with a history of Gilbert's syndrome, serum bilirubin assessments will be based on direct bilirubin.

8.4.2 Vital Signs

Markedly abnormal quantitative vital signs measurements will be identified in accordance with the predefined markedly abnormal criteria detailed in [Table 8-2](#).

Table 8-2 Vital Signs Markedly Abnormal Criteria

Variable	Unit	Low	High
Systolic Blood Pressure	mmHg	≤ 90 AND a decrease from baseline ≥ 20	≥ 180 AND an increase from baseline ≥ 20
Diastolic Blood Pressure	mmHg	≤ 50 AND a decrease from baseline ≥ 15	≥ 105 AND an increase from baseline ≥ 15
Pulse	Bpm	≤ 50 AND a decrease from baseline ≥ 15	≥ 120 AND an increase from baseline ≥ 15
Weight	Kg	Percentage decrease from baseline $\geq 7.0\%$	Percentage increase from baseline $\geq 7.0\%$

9 Study Population

The disposition of subjects enrolled in the trial will be described based on the Screened and Randomized Analysis Sets. All other tables and listings in this section will be based on the ITT Analysis Set, and all summaries and data listings will use treatment labels as specified in [Section 7.3](#). Summary tables will include columns for treatment groups and total.

9.1 Disposition of Subjects

The study is designed to conclude at least 365 days after the last subject is randomized.

Study visits are expected to be completed in person at all visits except visits 7 (Day 60) and 10 (Day 270) when visit completion by phone contact with subject is permitted. The investigator reports the type of contact at each visit, whether direct contact with subject (in-person or phone) or indirect based on contact with family member or care taker, or primary physician or medical record review, publicly available sources or other. A visit is considered to be complete if the type of contact is direct (in-person or phone) or with family member or care taker since it allows for full ascertainment of MACE. Otherwise, a visit will be considered to be incomplete.

The date of last MACE ascertainment will be derived for each subject and used in the analysis of time-to-event endpoints and count data. It is defined as the later of the last completed visit date or the date of the last positively adjudicated endpoint regardless of event

type. If a subject is missing both dates then the date of last MACE ascertainment will be set to the randomization date.

Subject disposition during the study will be summarized by treatment group and will include the information listed below:

Subject status:

- Number of subjects screened, number of screen failures, and number randomized
 - Of the number randomized, number of subjects receiving all four infusions, fewer than four infusions (discontinued and skipped dose) and no infusion
- Primary endpoint completion status - In order to be defined as a primary endpoint completer, one of the following conditions has to be met:
 - Ascertainment for MACE endpoint has been obtained through Study Day 90 or later or
 - Death prior to Study Day 90
 - Positively adjudicated primary composite MACE prior to Study Day 90
- Study completion status – In order to be defined as a study completer, one of the following conditions must be met:
 - The answer to the question “did the subject complete the last expected visit per study protocol?” at study conclusion is yes and direct contact with subject or indirect contact with family member or care taker is reported at Visit 11. Note: Assessment of study completion based either on medical records review, publicly available sources or any other method will not be considered as study completer in the analysis. The reason for discontinuation will be derived and displayed as due to indirect contact since full ascertainment of MACE cannot be considered as complete based on these methods of follow-up.
 - The answer to the question “did the subject complete the last expected visit per study protocol?” at study conclusion is no and reason for study withdrawal is reported as death in the eCRF.
- Reasons for study withdrawal will be presented in the order they are displayed in the eCRF with the following exceptions: study discontinuation due to death will not be reflected in this summary table as these subjects are considered to be completers in the analysis.

- Vital status will be summarized:
 - At Study Day 90
 - At study conclusion for subjects completing the study and
 - At Study Day 365 for subjects who discontinue from study participation prior to Study Day 365

Categories of study disposition status include completer, withdrawal of consent by subject, lost to follow-up, protocol deviation, or other. Complete withdrawal of consent prohibits further follow-up, including for vital status, unless allowed by local regulations. In lieu of complete withdrawal of consent, subjects may agree to limited or alternate methods of follow-up.

- In cases where only follow-up by medical record review is agreed to, the investigator will complete follow-up visits (according to the protocol defined visit schedule) based on medical record review to gather information on MACE outcomes. In such cases, investigator will report subject has completed participation in the study however the derived study conclusion will be 'no' and vital status at Study Day 365 of "Alive" will be derived.
- In cases where only follow-up to ascertain vital status at Visit 11 is agreed to: investigator will report that subject did not complete the study due to "other" reason. The investigator will further record the date subject was confirmed to be alive or dead in a free text field on the study conclusion eCRF page. The study day of confirmed to be alive or dead relative to randomization date will be computed and if greater than 365, vital status will be set to Alive. If date confirmed to be alive is less than 365 then vital status at day 365 will be set to Unknown. If date confirmed to be dead is less than 365 then vital status at day 365 will be set to dead.
- In case of complete withdrawal of consent, the date last known to be alive will be reported on the study conclusion eCRF page. A similar derivation as described in the previous paragraph will be applied to determine vital status at study day 365.
- Fraction of missing person years – the primary assessment of the extent of missing data will be based on the proportion of missing person years during the first 90 study days. For calculation of this proportion, subjects completing 90 days of follow-up or experiencing death prior to 90 days are assigned a score of 1 while subjects not completing 90 days of follow-up are assigned a score corresponding to the fraction of

the 90 day follow-up completed. The proportion of missing person years is defined as $1 - (\text{sum(score)}/n)$ where n is the total number of subjects.

A similar statistic will be presented to summarize the extent of missing person years through study day 365.

Analysis Sets:

- Number of subjects included in each of the analysis sets, described in [Section 6](#), will be summarized as counts and percentages

Sub-populations:

- Subjects in each subpopulation as defined by randomization strata will be summarized. The strata information from the eCRF as well as from the IRT system will be presented separately

Enrolment:

- Number randomized will be summarized by region, country, and site

Subject completion by visit:

- Number (%) of subjects completing each planned study visit will be summarized along with the type of contact. Visit completion is defined as direct contact with study participant (in person visit or phone with subject) or indirect contact with family member/care taker.

The following listings of individual subject data will be provided:

- Reason for screen failure as collected in the eCRF
- The listing of subjects discontinuing study treatment including reason
- Reasons for study withdrawal including the date of discontinuation
- Subjects excluded from the Randomized, ITT, mITT, and Safety Analysis Sets

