### **10.3.2.2      Primary Efficacy Endpoint**

The primary endpoint is defined as:

- Time to first occurrence of any component of the composite MACE, ie, CV death, MI, or stroke, from the time of randomization through 90 days.

All positively adjudicated MIs from randomization through 90 days will be included in the analysis of the primary endpoint. For each subject, time to event is defined as the time from randomization to the first occurrence of CV death, MI, or stroke based on CEC adjudicated and confirmed events. For subjects who do not have an event and do not complete the 90-day Follow-up Period, the censoring time is defined as the time from randomization to the last assessment at which it is confirmed that no event has occurred. For subjects who do not have an event or censoring time within the first 90 days after randomization, an administrative censoring will be applied at 90 days.

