10.1 Analysis of Primary Endpoint

The primary endpoint is defined as the time to first occurrence of any component of the composite MACE, ie, CV death, MI, or stroke, from the time of randomization through 90 days. This analysis will be based on events adjudicated and confirmed by the CEC. All adjudicated MIs from randomization through 90 days will be included in the analysis of the primary endpoint. A total of 1004 events for the primary composite endpoint are targeted as per the power calculation. However, the final analysis will include all events that are observed during the 90-day interval even if that number is larger or smaller than the target.

For each subject, time to event is defined as the time (number of days) from randomization to the first occurrence of confirmed CV death, MI, or stroke during 90 days of follow-up. For subjects without an event and last MACE ascertainment date occurring at least 90 days after randomization, an administrative censoring will be applied at 90 days. For subjects that experience a non-CV death prior to 90 days of follow-up, censoring will occur on the date of death. All other subjects will be censored on the last MACE ascertainment study day. The analysis of the primary endpoint will be based on positively adjudicated, CEC confirmed events occurring in the 90 days following randomization.

The estimand [ICH E9 (R1)], ie, the quantity to be estimated, in the primary analysis is defined as the hazard ratio for CSL112 vs. placebo, regardless of non-initiation, missed dose or discontinuation of treatment, in addition to standard of care as taken, for time to first occurrence of CV death, MI or stroke through 90 days in subjects with ACS presenting with STEMI or NSTEMI and MVD, while subjects have not died due to non-CV causes.

The following algorithm will be applied to derive two analysis variables, one corresponding to time in days and a second corresponding to censoring status. Any death with cause adjudicated as “undetermined” will be included as CV death in the primary analysis. The table below gives the derivation algorithm to be used in the primary analysis.

	Time to Event (days) [TTE]	Censoring Status [Censor]
First of confirmed CV death, MI, or Stroke during 90 days following randomization	(date of MACE – randomization date) + 1	0
Last MACE ascertainment on or after 90 days of follow-up without experiencing MACE	90	1

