10.2 Analysis of Key Secondary Endpoints

The key secondary endpoints will be analyzed based on the ITT population. The null hypothesis associated with each key secondary endpoint will be tested at the time of final analysis. The analysis will be based on CEC-adjudicated events and an assessment of concordance between the investigator-reported and CEC adjudicated events will be undertaken. Multiplicity adjustments are discussed in [Section 7.4](#).

The three key secondary endpoints and their planned analyses are given below:

10.2.1 Total number of hospitalizations for coronary, cerebral, or peripheral ischemia through 90 days after randomization

A negative binomial regression model will be fitted to the count data arising from the number of hospitalizations. This analysis will consider only those hospitalizations adjudicated by the CEC as meeting endpoint criteria. The model will include fixed effects for treatment, region, index MI type, and index MI management, age (as a continuous variable), diabetes, peripheral artery disease, and history of MI, and a term for interaction between index MI type and index MI management which correspond to the covariates in the primary analysis. The log link function will be used and the log-transformed duration of follow-up (based on the date of last MACE ascertainment) within 90 days will be included in the model to account for the variable duration of follow-up across subjects. However, if the model fails to converge then the offset statement will be excluded. The mean rate of hospitalization per 90 days will

be presented by treatment arm. A 1-sided P value for treatment comparison, the rate ratio (CSL112: placebo) and its 95% CI will be estimated from the model.

A cumulative plot of recurrent hospitalization events will be generated using a non-parametric estimator for the mean cumulative function (MCF). Nelson [[Nelson, 2003](#)] introduced the MCF as a way to summarize the average number of events occurring in a subject by time t , within a population exposed to censoring events such as losses to follow-up and termination of the study. It assumes non-informative censoring and the risk set decreases only when an individual is removed from follow-up. A supportive data listing of hospitalization data will be produced.

The SAS code for fitting a negative binomial regression model to the count data from hospitalizations is given in [Appendix 15.5](#).

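### For subjects followed only through records, physicians or public sources, the SAP counts the MACE found there but discards most of the event-free time, which biases event rates upward

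*SAP*

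**What the plan says.** - **Completed visits (SAP 9.1).** "A visit is considered to be complete if the type of contact is direct (in-person or phone) or with family member or care taker". "Otherwise, a visit will be considered to be incomplete". Contact with the primary physician, medical-record review, public sources and other routes fall in the second group.
- **Ascertainment date (SAP 9.1).** It is "the later of the last completed visit date or the date of the last positively adjudicated endpoint regardless of event" type. Its use is general: "The date of last MACE ascertainment will be derived for each subject and used in the analysis of time-to-event endpoints and count data".
- **Record-only follow-up (SAP 9.1).** Where a subject agrees only to record review, "the investigator will complete follow-up visits (according to the protocol defined visit schedule) based on medical record review to gather information on MACE outcomes".
- **Primary endpoint (SAP 10.1).** The first CEC-confirmed CV death, MI or stroke within 90 days is an event. Neither the source of the information nor the last completed visit limits this. Subjects with ascertainment to Day 90 are censored at Day 90 and non-CV deaths at the date of death. "All other subjects will be censored on the last MACE ascertainment study day". SAP 10.2.2 and 10.2.3 carry the approach to 180 and 365 days.
- **Hospitalizations (SAP 10.2.1).** The negative binomial offset is the "log-transformed duration of follow-up (based on the date of last MACE ascertainment) within 90 days".
- **Protocol 10.3.2.2.** For subjects without an event who do not complete 90 days, "the censoring time is defined as the time from randomization to the last assessment at which it is confirmed that no event has occurred". Contact type is not mentioned. SAP Section 5 records no change from the protocol's planned analyses.

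**The concern.** Take two subjects whose last completed visit is Day 29 and who then allow record review only. Subject A has an MI on Day 70, found in the records and confirmed: an event on Day 70. Subject B's records are reviewed at the Day 90 visit and show nothing: B is censored on Day 29. Both were observed in the same way, but the time after Day 29 is kept only for the one who had an event.

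Cox and Kaplan-Meier analyses assume that whether a subject stays in the risk set does not depend on what happens next. For this subset it does. The numerator keeps the subset's events while the denominator loses most of its person-time, so estimated rates rise in each arm that has such subjects. At stake are the event rates reported for the primary and two key secondary MACE endpoints, the hospitalization rates and, if the arms differ in this kind of follow-up, the hazard ratio.

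**Working it through.** **Plan's own figures.** SAP 4.5 assumes a 90-day placebo rate of 6.4% and a hazard ratio of 0.80, with 1004 events and 17,400 subjects. The pooled rate is (6.40 + 5.12)/2 = 5.76%, and 1004/0.0576 = 17,431, within 0.2% of 17,400. A simulation of the four looks gives 91.95% power against the stated 91.9%. The baseline is therefore sound. The plan gives no figure for the censoring rule or for the share of subjects it touches.

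**Assumptions not in the documents.** q = share whose contact is record-type only after day c, the last completed visit; s = share of their MACE that is found; constant hazard λ; the switch is unrelated to risk. At 8700 per arm, q of 1% to 5% is 87 to 435 subjects.

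**Hazard estimated after day c:**

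- SAP rule: events come from (1−q) + qs of subjects, but the risk set is close to (1−q). Estimate ≈ λ[1 + qs/(1−q)], too high for any s > 0.
- Rule (a), events and time both end at the last completed visit: λ(1−q)/(1−q) = λ.
- Rule (b), both counted through the last visit by any source: about λ[1 − q(1−s)], correct if s = 1 and too low otherwise.

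**90-day placebo rate.** The cumulative hazard is −ln(1 − 0.064) = 0.06614, of which 61/90 = 0.678 falls after Day 29. With q = 5% and s = 1: 0.06614 × (1 + 0.678 × 0.05/0.95) = 0.0685, and 1 − exp(−0.0685) = 6.62%. A daily-grid calculation, which also keeps in the risk set the switched subjects who later have an event, gives for a true rate of 6.40% and s = 1:

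| Last completed visit | q = 1% | q = 2% | q = 5% | q = 10% |
|---|---|---|---|---|
| Day 1 | 6.46% | 6.52% | 6.71% | 7.05% |
| Day 29 | 6.44% | 6.48% | 6.62% | 6.85% |
| Day 60 | 6.42% | 6.44% | 6.51% | 6.63% |

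If records find half the events, the excess roughly halves (q = 5%, Day 29: 6.51%). A front-loaded hazard changes these figures by at most about 0.1 point. Rule (a) returns 6.40% throughout. Rule (b) returns 6.40% with s = 1, and 6.36% with s = 0.5, q = 2%, Day 29.

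**365 days.** Assuming a true rate of 10% and a switch after Day 90, q = 2%, 5% and 10% give 10.14%, 10.36% and 10.76%.

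**Hazard ratio (Day 29, s = 1):**

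| True HR | q placebo | q CSL112 | Estimated HR |
|---|---|---|---|
| 0.80 | 1%, 2% or 5% | same | 0.800 |
| 0.80 | 1% | 2% | 0.806 |
| 0.80 | 2% | 5% | 0.817 |
| 0.80 | 5% | 2% | 0.784 |
| 1.00 | 5% | 2% | 0.979 |

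The standard error of the log hazard ratio at 1004 events is about 2/√1004 = 0.063. The 1%/2% row is a shift of ln(0.8055/0.8) = 0.007, or 0.11 standard errors. The 2%/5% row is ln(0.8170/0.8) = 0.021, or 0.33. Both symmetric rules return the true value (checked with s = 1).

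**Hospitalization offset.** Give A a hospitalization on Day 70 instead of the MI. A then contributes 1 event over 70 days and B contributes 0 over 29: one event in 99 days. Counting both subjects through Day 90 gives one event in 180 days; cutting both at Day 29 gives none in 58.

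**The case against.** The SAP has a reason for its visit definition. It holds that direct or family contact ascertains MACE fully and that record or public-source follow-up does not, which is a fair reading of the protocol's requirement that absence of an event be confirmed. Crediting record-only time has its own cost if records miss events, as the 6.36% shows. This stands as a case against treating record review as equal to a visit, and a reader who inferred a flat contradiction of Protocol 10.3.2.2 would go too far. But the reason supports leaving out both the events and the time from such sources. It does not support keeping only the events.

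Three other stronger readings are not supported.

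- **The primary hazard ratio is biased.** The documents give no share of such subjects and no ground, in a double-blind trial, to expect a difference between arms. Equal shares and equal event-finding leave the ratio at 0.800.
- **Everyone who leaves in-person follow-up is affected.** Phone, family and care-taker contacts count as completed visits. A later completed visit restores the earlier time, as does a later positively adjudicated endpoint up to its date. Non-CV deaths are censored at death. All-cause death is largely protected by the Day 365 vital-status rule in SAP 10.3.
- **Deaths traced in public sources after full withdrawal generally count.** SAP 9.1 says full withdrawal bars further follow-up unless local rules allow it, and the opening of SAP Section 10 only lists endpoints reported and adjudicated after the study conclusion date.

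Planned safeguards help in part. Visit completion by contact type is to be summarized by treatment group, so an imbalance would be visible. The tipping-point analyses at 90 and 365 days do not remove the asymmetry: they impute further events for subjects censored event-free, while the events of their record-followed counterparts are already counted.

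**Conclusion.** The asymmetry follows from the SAP's text and needs no assumption. For the affected subset it makes follow-up depend on outcome, biases MACE rates upward at 90, 180 and 365 days, and distorts the hospitalization offset.

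The size is unknown. With 1% to 5% moved after Day 29, all their events found, a constant hazard and a switch unrelated to risk, the excess is about 0.04 to 0.2 percentage points on 6.40%, and smaller if records miss events. The effect on the hazard ratio is conditional: essentially nil with equal shares and event-finding, in either direction otherwise. The rule should be corrected because it is biased as written and cheap to repair. The documents do not show that the primary test is compromised.

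**What to change.** Apply one cutoff to events and to event-free time, by one of two rules:

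- **(a) End both at the last completed visit.** State in SAP 10.1, 10.2.2 and 10.2.3 that later events from incomplete-contact follow-up are not counted, and amend the SAP 10.1 statement that all events observed in the 90-day interval enter the final analysis. Removing the endpoint clause from SAP 9.1 would not be enough, because SAP 10.1 counts confirmed events independently of that date.
- **(b) Count both through the last follow-up visit by any permitted source,** including public sources if their events count.

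Pre-specify one rule as the lead, or at minimum as a sensitivity analysis, and run the other alongside. Use the same date for the hospitalization counts and offset. Report by arm the number of subjects followed this way and their events. Reconcile the wording with Protocol 10.3.2.2 and SAP Section 5.

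The cost is SAP text and a derivation, since contact type is already reported at each visit. The documents do not show that the date through which records were reviewed is captured, so (b) should rest on the visit date. Each rule has a downside to state: (a) drops some confirmed events and assumes the switch is unrelated to risk; (b) is biased low if records miss events.
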